7. INTERVENTIONS

The new procedure

All patients will have their left atrial geometric volume reduced, pulmonary vein island isolated and left appendage ligated or suture closed. After the superior vena cava was transected, two circular incisions were usually made in the left atrial wall between the pulmonary veins and the mitral annulus for circumferential atrial strip resection and pulmonary vein island isolation. The first circular incision was performed around the pulmonary veins. With this incision, pulmonary vein island was isolated and the left atrium was opened. The second one was performed in the interatrial groove and extended around the mitral annulus, leaving a 2 cm inferior wall margin from the annulus and the appendage in situ. With those two incisions, a circumferential strip of the left atrium was excised. Then the base of the left atrial appendage was ligated or excised and sutured. After the mitral manipulations, the center of the pulmonary vein island was longitudinally reef-imbricated with a 3-0 polypropylene continuous running suture to exclude toward the outside of the left atrial cavity. This plicated pulmonary vein island was directly anastomosed to the resected margin around the mitral annulus and the intraatrial septum instead of the interatrial groove. Finally, caval continuity was restored after aortic cross-clamp removal using a running 4-0 polypropylene suture.

Mitral Valve Surgery

For mitral regurgitation, the procedures will be a valve repair in the majority of cases. For valves that are not amenable to repair, and for most cases of mitral stenosis, a valve replacement will be performed. And the cardiopulmonary bypass time will be recorded.

Transthoracic Doppler Echocardiography

Transthoracic Doppler Echocardiography(TDE) will be used to measure left atrial size and volumes, quantify mitral valve function, detect intracardiac thrombi, and to assess left atrial and left ventricular function. TDE will be used to measure LA size as well as diameters in LA.

Electrocardiogram (ECG)

An ECG will be done upon arrival in the operating room. This tracing will be used to assess heart rhythm on all patients and provide part of the documentation needed to establish the diagnosis of longstanding persistent AF.

Postoperative management

Standardization of Anti-arrhythmic Drug Use during Follow-up

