Physicians must document in the Medical History Form the timing and duration of AF. An ECG or other direct assessment of heart rhythm will be obtained within 1 year prior to document the presence of long-standing persistent AF. All long-standing persistent AF patients will undergo an ECG upon arrival in the operating room (OR). Furthermore, there will be a baseline transthoracic Doppler echocardiogram performed within 3 months prior to surgery.

Data collected during hospitalization

Informed consent

A detailed explanation of the risks and benefits of the study will be outlined by the investigator to each patient or their legally authorized representative before any preoperative assessments that are not part of the routine preparation and they will be asked to sign a consent form.

Surgical Procedures

Initial surgical intervention and event driven

Includes information regarding specific primary procedure, operative variables, lesion sets created, additional procedures performed at time of initial operation, intra-operative pharmacological agents, intra-operative blood transfusions, the cardiopulmonary bypass time.

Medications

All cardiovascular medications are recorded, including amiodarone given prophylactically since surgery.

Physical Examination (including vital signs and cardiopulmonary examination)

Electrocardiogram (12-lead ECG)

Adverse Events

Detailed information regarding adverse events is recorded at the time an event occurs during hospitalization. Investigators are asked to make a judgment as to the seriousness and relationship of the event to the surgical intervention.

Patient Discharge

Patients clinically stable for discharge may be discharged to an affiliated rehabilitation center, intermediate care center, long-term care facility, step-down facility or home.

Data collected at follow-up

Follow-up visits will be conducted at 30 days, 3 months, 6 months and 12 months after surgery (± 30 days) after surgery provided that the patient is still alive. The following assessments are scheduled at each visit:

Transthoracic Doppler Echocardiogram

All patients will undergo follow-up transthoracic Doppler echocardiography at the investigative center*. Transthoracic Doppler echocardiography will be used to measure LA function (a) atrial filling, (b) LA ejection fraction, (c) atrial systolic mitral annular velocity (TDI). MV function, mitral regurgitation and LV function will be measured.

24-hour Holter Monitoring

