The 24-hour holter monitoring provided to patients will be used for this assessment.

Medications

All cardiovascular, inotropic, antiplatelet agents, and anticoagulants will be recorded. Medications (including AADs) will be recorded at the study visit, and also as indicated at the time of associated adverse events. Response to DC cardioversions (success or failure) will also be recorded.

Functional Status

NYHA classification will be determined by a coordinator or physician not otherwise involved in this trial and blinded to the treatment assignment. The NYHA class will be documented on the "New York Heart Association Classification" form.

Adverse Events, Anti-arrhythmic Interventions, and Hospitalizations

Patients will be asked to recall any adverse events (including stroke and bleeding) and the number of hospitalizations that occurred out of network since the last contact. Patients will also be asked if they had a permanent pacemaker insertion, cardioversion or subsequent ablation since the last contact.

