peripheral embolism, coronary artery injury, anatomical excessive bleeding, deep sternal wound infection/mediastinitis, damage to specialized conduction system requiring permanent pacemaker, and superior vena cava stenosis, within 30 days post-procedure or hospital discharge (whichever is later). The rate of these safety endpoints will be calculated within 30 days after surgery.

Secondary Analyses

Efficacy

(a) The size and shape of left atrium. The anteroposterior, transversal, and superoinferior diameters, as well as their ratios, of left atrium between two time points (i.e., before surgery and 12 months post-surgery), will be measured by transthoracic echocardiography. The absolute change and reduction rate of each diameter will be analyzed, and the post-surgery size and shape will be compared with Chinese standards.

(b) Left ventricular ejection fraction and peak late transmitral flow velocity (A) at 12 months post-surgery will be measured by transthoracic echocardiography. These measurements evaluate the function of heart pump.

Safety

(a) Major adverse cardiac events (MACE) defined as a non-weighted composite score of: death, stroke, worsening heart failure (+1 NYHA Class), CHF hospitalization, and mitral valve [MV] re-intervention within 12 months of surgery. The rate of MACE will be calculated and compared with MACE rate historically reported in COX MAZE IV procedure.

(b) Incidence of protocol-defined and serious adverse events (especially thromboembolic and hemorrhagic events) within 12 months of surgery. The rate of SAE will be calculated and compared with MACE rate historically reported in COX MAZE IV procedure.

(c) All-cause mortality at 12 months post-surgery. The Kaplan-Meier curve will be plotted to show the probability of death at a respective time interval and compared with 1-year deaths historically reported in COX MAZE IV procedure.

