13. SPECIFIC ADVERSE EVENT DEFINITIONS

Bleeding

A bleeding event is defined by any one of the following:

- Transfusion of > 2 units RBC within the first 24 hours following surgery
- Death due to hemorrhage
- Re-operation for hemorrhage or tamponade

NOTE: Hemorrhagic stroke is considered a neurological event and not as a separate bleeding event.

Cardiac Arrhythmias

Any documented arrhythmia that results in clinical compromise (e.g., hemodynamic compromise, oliguria, pre-syncope or syncope) that requires hospitalization or requires a physician visit or occurs during a hospital stay.

Cardiac arrhythmias are classified as:

1. Sustained ventricular arrhythmia requiring defibrillation or cardioversion
2. Sustained supraventricular arrhythmia requiring drug treatment or cardioversion
3. Cardiac conduction abnormalities requiring permanent pacemaker

Pericardial Fluid Collection

Accumulation of fluid or clot in the pericardial space that requires surgical intervention or percutaneous catheter drainage. This event will be subdivided into those with clinical signs of tamponade (e.g. increased central venous pressure and decreased cardiac output) and those without signs of tamponade.

Pleural Effusion

Accumulation of fluid or clot in the pleural space documented by chest radiogram or chest CT that requires evacuation with surgical intervention or chest tube placement.

Atrial Rupture

Disruption in the integrity of the left or right atrial wall, documented by direct inspection or diagnostic testing, that necessitates surgical repair.

Valvular Injury

Injury to a cardiac valve (excluding the mitral valve), as evidenced by new regurgitation or stenosis following the treatment intervention. This definition excludes changes to the mitral valve because it will be surgically repaired at the time of the treatment intervention.

Non-infectious Pericarditis

Signs and symptoms of pericardial inflammation, with or without electrocardiographic evidence, requiring pharmacologic anti-inflammatory therapy. This definition excludes infectious pericarditis (see Major Infection infectious pericarditis definition below).

Superior vena cava Stenosis

A \geq 50% decrease in the diameter of the superior vena cava as documented by echocardiography.

Diaphragmatic Paralysis

Phrenic nerve injury as evidenced by new elevation of a hemi-diaphragm on chest radiogram.

Pneumothorax

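### Superior vena cava diameter is on no echo measurement list, although a fall in it defines a primary safety component; the reference NYHA class is likewise unspecified

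*Combined protocol and SAP*

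**What the plan says.** **Superior vena cava.** Section 7 (The new procedure) describes the left atrial incisions as made "After the superior vena cava was transected", with the vessel sutured back together at the end. Section 13 defines stenosis as a "decrease in the diameter of the superior vena cava as documented by echocardiography" of at least 50%. Section 12 lists it last in the primary safety composite: "superior vena cava stenosis, within 30 days post-procedure or hospital discharge (whichever is later".

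**Echocardiography.** Section 9 states that "there will be a baseline transthoracic Doppler echocardiogram performed within 3 months prior to surgery", and schedules echo at each follow-up visit (30 days, 3, 6 and 12 months, with a 30-day tolerance). Section 7 says that echo "will be used to measure left atrial size and volumes, quantify mitral valve function, detect intracardiac thrombi", and assess left atrial and left ventricular function; it adds that "TDE will be used to measure LA size as well as diameters in LA". The follow-up list in Section 9 reads "Transthoracic Doppler echocardiography will be used to measure LA function (a) atrial filling, (b) LA ejection fraction, (c) atrial systolic mitral annular velocity (TDI", followed by mitral valve function, regurgitation and left ventricular function. The SVC is in neither list.

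**NYHA class.** A worsening of one class is part of MACE (Sections 8 and 12). The heart failure definition in Section 13 also uses a worsening of at least one class, and heart failure belongs to the primary safety composite. Under the follow-up assessments, Section 9 says that "NYHA classification will be determined by a coordinator or physician not otherwise involved in this trial". The admission data in the same section do not name NYHA class.

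**The concern.** Both events are defined by a decline, so each needs a reference value and a later value measured in the same way. For the SVC the plan asks for neither. For NYHA class it asks only for the later one.

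The SVC part matters more. A stenosis that causes symptoms may be investigated and reported; one that does not can meet the definition only if someone measures the vessel. The study has a single arm, and Section 4 hypothesizes fewer early adverse outcomes than were historically reported with Cox-Maze IV. Under-counting an event that arises from the new procedure itself would favour that hypothesis, and no concurrent arm would share the error.

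**Working it through.** The plan states no figure for either component, so the check is mainly a comparison of what each definition needs with what is scheduled.

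**1. SVC stenosis**

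| Needed to score the event | What the plan provides |
|---|---|
| A pre-operative echo | Yes: within 3 months before surgery (Section 9) |
| SVC diameter on that echo | Not listed (Sections 7 and 9) |
| A post-operative echo near the end of the composite window | Yes: 30-day visit (Section 9) |
| SVC diameter on that echo | Not listed (Sections 7 and 9) |
| A named reference for the 50% fall | Not stated (Section 13) |

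The other routes to detection do not close the gap. Section 9 records adverse events as they occur in hospital and asks patients at visits to recall events. In Section 11 the Clinical Events Committee reviews events that have been reported. An unmeasured, symptom-free narrowing enters none of these.

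**2. Possible size of the SVC effect**

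Let *s* be the proportion of patients with asymptomatic stenosis, *d* the share of them detected anyway, and *o* the share of the undetected who already have another component event. The downward error in the composite rate is

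error = s × (1 − d) × (1 − o).

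None of the three is in the documents. With N = 120, one missed patient with no other component event is worth 1/120 = 0.83 percentage points. As an assumption only, take s from 2% to 10% with d = 0 and o = 0. The error is then 2 to 10 percentage points, or 0.02 × 120 = 2.4 to 0.10 × 120 = 12 patients. For each assumed *s* this is an upper bound, since any detection or overlap makes it smaller.

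**3. Timing**

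The primary window closes at 30 days or discharge, whichever is later. Echoes at 3, 6 and 12 months would ordinarily fall outside it, so only the 30-day echo can serve. If the 30-day tolerance applies to that visit, it can fall anywhere up to day 60, which may also be after the window has closed.

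**4. NYHA class**

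If the reference class is recalled or reconstructed, worsening can be missed or created. With true rate π, sensitivity Se and specificity Sp,

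observed = Se × π + (1 − Sp) × (1 − π).

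All inputs below are assumptions; expected events are for N = 120.

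| π (events) | Se 50%, Sp 100% | Se 80%, Sp 95% |
|---|---|---|
| 2% (2.4) | 1.0% (1.2) | 6.5% (7.8) |
| 5% (6.0) | 2.5% (3.0) | 8.75% (10.5) |
| 10% (12.0) | 5.0% (6.0) | 12.5% (15.0) |

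For π = 5% in the last column: 0.80 × 0.05 + 0.05 × 0.95 = 0.04 + 0.0475 = 0.0875. The observed rate lies below the true rate in one scenario and above it in the other, so the direction of the error is not determined.

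**The case against.** **The echo lists may not be exhaustive.** The follow-up list in Section 9 also omits the three left atrial diameters, yet Section 8 makes them a secondary endpoint. Omission from one list therefore does not prove that a quantity goes unmeasured. The principle is fair, but the comparison fails: the left atrial diameters are called for in Sections 7 and 8, whereas no section asks for the SVC diameter. Naming echo as the method in Section 13 does not schedule the measurement.

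**The definition need not mean change from baseline.** Section 13 names no reference, so the fall could be judged against an adjacent segment on one post-operative image. This ambiguity stands. It removes the need for a baseline value but not for a post-operative one, which is also unlisted.

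**Baseline data exist.** A reader might infer that no baseline assessment is planned. The documents do not support that. A baseline echo is scheduled, and the history form covers current condition with an explicitly open list. Baseline NYHA class is unspecified, not shown to be absent. Section 10 also retains source data and test reports, so some SVC diameters might be recoverable; the documents do not say whether stored images could be re-measured.

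**Some heart failure events need no reference class.** MACE includes heart failure hospitalization, and the Section 13 definition includes new-onset signs or symptoms. This stands and limits the reach of the NYHA gap.

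**No test is attached.** Section 12 only calculates the primary safety rate, without a threshold. This lowers the stakes, but the hypothesis in Section 4 still invites a comparison with historical rates.

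**Conclusion.** The point holds for the SVC component. As written, the plan names an event specific to its own operation, defines it by a measured diameter, and schedules that measurement nowhere. Asymptomatic stenosis would probably go uncounted, and the primary safety rate would tend to be too low. This rests on following the measurement lists as they stand and on treating a patient without a measurement as event-free. The size cannot be derived from the documents; the 2 to 10 percentage points above only restate an assumed rate.

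The NYHA point is secondary. The reference class is unspecified, and this touches both MACE and the primary composite. A reader might infer that both components are bound to be under-detected. That does not follow for NYHA class, where the error can go either way, and for the SVC it is probable rather than certain.

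The composite as a whole remains usable. One of its components cannot be scored reliably without the change below.

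**What to change.** - Add SVC diameter to the baseline echo and to the 30-day echo, both already scheduled.
- In Section 13, name the pre-operative diameter as the reference for the 50% fall, and score the primary component from that pair.
- State in advance how a 30-day echo done after the composite window has closed is counted.
- Where either diameter cannot be obtained, report the component as not assessable rather than as no event, and give the number of patients with a complete pair.
- Report SVC diameters from the 3-, 6- and 12-month echoes only as 12-month safety data, outside the primary composite.
- Record the pre-operative NYHA class at admission, and name it as the reference for both the MACE component and the heart failure definition. Using an assessor of the kind Section 9 requires at follow-up would keep the two readings comparable, but this is a preference.

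The cost is one extra measurement on echoes already planned and one admission field, with no extra visit or procedure. Transthoracic echo may not give a usable SVC diameter in every patient; the documents do not address this. The reported safety rate may also turn out less favourable.
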